## CLINICAL TRIAL PROTOCOL SYNOPSIS

Company name	Boehringer Ingelheim
Original Protocol date	20 Dec 2021
Revision date	21 Aug 2023
BI trial number	1366-0029
Title of trial	Randomised, open-label and parallel group trial to investigate the effects of oral BI 685509 alone or in combination with empagliflozin on portal hypertension after 8 weeks treatment in patients with clinically significant portal hypertension (CSPH) in compensated cirrhosis
Coordinating Investigator	Univ.-[name], MD, PhD [REDACTED]
Trial site(s)	Multi-centre trial
Clinical phase	II
Trial rationale	In this Phase II trial, the efficacy of treatment in patients with CSPH (defined by the presence of varices and hepatic venous pressure gradient [HVPG] $\geq$ 10 mmHg), in compensated cirrhosis due to hepatitis B virus (HBV), hepatitis C virus (HCV) and non-alcoholic steatohepatitis (NASH) with or without type 2 diabetes mellitus (T2DM) will be assessed. The trial will evaluate the short-term efficacy of BI 685509 alone and in combination with empagliflozin, where patients will be treated for 8 weeks and the portal pressure will be assessed quantitatively via HVPG measurements. The trial will also provide supportive evidence for the planned Phase III development.
Trial objective(s)	The trial will investigate the safety and tolerability, of BI 685509 and the combination of BI 685509 with empagliflozin, on top of standard of care, on portal hypertension in patients with clinically significant portal hypertension in compensated cirrhosis. The primary objective is to estimate the percentage change in HVPG from baseline measured after 8 weeks in patients with HBV, HCV and NASH with or without T2DM.
Trial endpoints	The primary endpoint is the percentage change in HVPG from baseline (measured in mmHg) after 8 weeks of treatment. Secondary endpoints include: 

• occurrence of a response, which is defined as <math>> 10\%</math> reduction from baseline HVPG (measured in mmHg) after 8 weeks of treatment

• occurrence of one or more decompensation events (i.e. ascites, variceal haemorrhage [VH], and / or overt hepatic encephalopathy [HE]) during the 8 week treatment period

Proprietary confidential information © 2023 Boehringer Ingelheim International GmbH or one or more of its affiliated companies

	

occurrence of CTCAE grade 3 (or higher) hypotension or syncope based on Investigator judgement, during the 8 week treatment period

occurrence of discontinuation due to hypotension or syncope during the 8 week treatment period

Trial design	Randomised, open-label and parallel design comparison of four groups over 8 weeks
Total number of patients enrolled	80
Number of patients per treatment group	Approximately 20
Diagnosis	Patients with CSPH in compensated cirrhosis due to HBV, HCV, and NASH with or without T2DM
Main inclusion and exclusion criteria	
Main inclusion criteria
 

male or female who is <math>\geq 18</math> (or who is of legal age in countries where that is greater than 18) and <math>\leq 75</math> years old at screening (Visit 1a)

clinical signs of CSPH as described by either one of the points below:

documented endoscopic proof of oesophageal varices and / or gastric varices at screening (Visit 1b) or within 6 months prior to screening (Visit 1b)

documented endoscopic-treated oesophageal varices as preventative treatment

CSPH defined as baseline HVPG <math>\geq 10</math> mmHg (measured at Visit 1c), based on a local interpretation of the pressure tracing

diagnosis of compensated cirrhosis due to HBV, HCV or NASH with or without T2DM. Diagnosis of cirrhosis must be based on histology (historical data is acceptable) or on clinical evidence of cirrhosis (e.g. platelet count <math>< 150 \times 10^9/L</math> [<math>150 \times 10^3/\mu L</math>], nodular liver surface on imaging or splenomegaly etc.)

willing and able to undergo HVPG measurements per protocol (based on Investigator judgement)

if receiving statins, must be on a stable dose for at least 3 months prior to screening (Visit 1b), with no planned dose change throughout the trial

if receiving NSBBs or carvedilol, must be on a stable dose for at least 1 month prior to screening (Visit 1b), with no planned dose change throughout the trial

if receiving pioglitazone, GLP1-agonists, or vitamin E must be on a stable dose for at least 3 months prior to screening (Visit 1b), with no planned dose change throughout the trial

 
Main exclusion criteria

Proprietary confidential information © 2023 Boehringer Ingelheim International GmbH or one or more of its affiliated companies

	

previous clinically significant decompensation events (e.g. ascites [more than perihepatic ascites], VH and / or apparent HE)

history of other forms of chronic liver disease (e.g. alcohol-related liver disease, autoimmune liver disease, primary biliary sclerosis, primary sclerosing cholangitis, Wilson's disease, haemachromatosis, alpha-1 antitrypsin [A1AT] deficiency)

patients without adequate treatment for HBV, HCV, or NASH (e.g. antiviral therapy in chronic HBV or HCV or lifestyle modification in NASH)

if received curative anti-viral therapy for HCV, no sustained virological response (SVR) or SVR sustained for less than 2 years prior to screening or if HCV RNA detectable

if receiving anti-viral therapy for HBV less than 6 months prior to screening, if dose of anti-viral therapy not stable in the 6 months prior to screening, if planning a dose change during the trial or if HBV DNA detectable

weight change <math>\geq 5\%</math> within 6 months prior to screening

SBP <math>< 100</math> mmHg and DBP <math>< 70</math> mmHg at screening (Visit 1a)

Model of End-stage Liver Disease (MELD) score of <math>> 15</math> at screening (Visit 1a)

hepatic impairment defined as a Child-Turcotte-Pugh score <math>\geq</math> B8 at screening (Visit 1a)

ALT or AST <math>> 5</math> times upper limit of normal (ULN) at screening (Visit 1a)

eGFR (CKD-EPI formula) <math>< 20</math> mL/min/1.73 m^2 at screening (Visit 1a)

alpha-fetoprotein <math>> 50</math> ng/mL (<math>> 50</math> <math>\mu</math>g/L) at screening (Visit 1a)

history of clinically relevant orthostatic hypotension, fainting spells or blackouts due to hypotension or of unknown origin (based on Investigator judgement)

Current or planned SGLT2i / SGLT-1/2i treatment

Type 1 Diabetes Mellitus

Test product(s)	BI 685509 Empagliflozin
dose	Treatment group 1, 2, 3: [REDACTED] BI 685509 BID (maintenance dose) Treatment group 4: [REDACTED] BI 685509 BID (maintenance dose) + 10 mg Empagliflozin QD
mode of administration	Oral
Comparator product(s)	Not applicable

Proprietary confidential information © 2023 Boehringer Ingelheim International GmbH or one or more of its affiliated companies

dose	Not applicable
mode of administration	Not applicable
Duration of treatment	8 weeks
Statistical methods	For the primary endpoint, an analysis of covariates (ANCOVA) model will be used to obtain adjusted means for the treatment effects in the full analysis set (FAS). This model will include treatment as a fixed classification effect and baseline HVPG as a linear covariate. The random error is assumed to be normally distributed with mean 0 and variance $\sigma^2$ . The analysis will only be used for estimation of treatment effects without performing statistical tests. Secondary and further endpoints will be analysed descriptively. Safety analyses will be performed using BI standards and will be descriptive in nature.

Proprietary confidential information © 2023 Boehringer Ingelheim International GmbH or one or more of its affiliated companies

## FLOW CHART

Trial Periods	Screening 			Randomised Treatment						Follow-Up
	1a 	1b 	1c 	2 	3	4	5	6	EoT / ED 	
Visit	1a 	1b 	1c 	2 	3	4	5	6	EoT / ED 	EoS 
Week	-6			R	1	2	4	6	8	12
Day	-42			1	8	15	29	43	57	85
Time window for visits (days)	See footnote 1			N/A	+ 2	+ 2	+ 2	± 3	± 5	± 5
Fasting status 	NF	F	F	F	NF	NF	F	NF	F	F
Informed consent	x									
Register patient in IRT system via IRT call	x									
Demographics 	x									
Medical history / baseline conditions 	x									
Concomitant therapy	x	x	x	x	x	x	x	x	x	x
Anthropometric measures 	x			x	x	x	x	x	x	x
Vital signs 	x			x 	x 	x 	x 	x	x	x
Physical examination 	x 			(x)	(x)	(x)	(x)	(x)	x	(x)
Resting 12-lead ECG 	x			x 	x 	x 	x 	x	x	x
Safety laboratory sampling	x			x	x	x	x		x	x
Pregnancy testing 	x s			x u			x u		x u	x u
Gastroscopy 		x								
Hepatic venous pressure gradient (HVPG) 			x						x	
Ultrasound (liver and spleen) 		x					x		x	x
Review of in-/exclusion criteria	x	x	x	x						
Randomisation				x						
IRT call				x	x	x	x	x	x	

Proprietary confidential information © 2023 Boehringer Ingelheim International GmbH or one or more of its affiliated companies

FLOW CHART (cont)

Trial Periods	Screening 			Randomised Treatment						Follow-Up
	1a 	1b 	1c 	2 	3	4	5	6	EoT / ED 	
Visit										
Week		-6		R	1	2	4	6	8	12
Day		-42		1	8	15	29	43	57	85
Time window for visits (days)	See footnote 1			N/A	+ 2	+ 2	+ 2	± 3	± 5	± 5
Fasting status 	NF	F	F	F	NF	NF	F	NF	F	F
Dispense trial medication				x	x	x	x	x		
Dose-titration 				x	x	x				
Train patient (home BP and HR monitoring) 				x	(x)					
Home BP and HR monitoring (by patient) 				x	→	→	→	→	→	
Biobanking sampling 				x					x	
All AEs / SAEs / AESIs 	x	x	x	x	x	x	x	x	x	x
Collect returned trial medication					x	x	x	x	x	
Compliance check					x	x	x	x	x	
End of trial medication									x	
Completion of patient participation										x

Footnotes:

1. The screening period consists of 3 visits (Visits 1a/b/c). These visits should ideally be completed within a period of 4 weeks, but a maximum of 6 weeks (-42 days) will be permitted. There is no minimum duration. A patient can proceed from one visit to the next as soon as all results from the previous visit are available and if he / she remains eligible for the trial. Visit 1b and 1c can be performed on the same day; in that case, the gastroscopy must be performed prior to the HVPG measurement. The ultrasound [REDACTED] can be performed at either Visit 1b or 1c. Refer to Sections , [5.1.2](#), [5.2.5.1](#), [5.2.5.2](#) and [6.2.1](#)

Proprietary confidential information © 2023 Boehringer Ingelheim International GmbH or one or more of its affiliated companies

2. Visit 2 = enrolment / randomisation / Day 1 of trial medication. All assessments at this visit (excluding post-dose ECGs [redacted] [refer to Sections [5.2.4](#), [6.2](#) and [Appendix 10.1](#)]) should be completed before the first dose of trial medication is administered
3. Patients who complete 8 weeks of treatment will have an End of Treatment (EoT) visit, followed 4 weeks later by an End of Study (EoS) visit. The last dose of trial medication will be administered in the evening of the day before the EoT visit. Patients who discontinue trial medication prematurely will have an Early Discontinuation (ED) visit completed instead of the planned treatment period visit. The ED visit should be performed within 7 days of discontinuing the trial medication, followed 4 weeks later by an EoS visit. Refer to [Section 6.2.2.1](#) for details of assessments that should be performed during an ED visit and the EoS visit that follows it.
4. Fasting status: F = fasting (i.e. overnight fast, no food or drink, except water), NF = non-fasting
5. For further details refer to [Section 6.2.1](#)
6. Anthropometric measures = height (measured at Visit 1a only), weight, and waist and hip circumference. Refer to [Section 5.2.1.1](#)
7. Measurement of vital signs should precede the 12-lead ECG, and measurement of the 12-lead ECG should precede blood sampling and intake of trial medication at visits where a single ECG is required. The 12-lead ECG should be performed after the patient has rested for at least 5 minutes in a supine position. From Visit 2 onwards, the patients home BP monitoring equipment should be used in the clinic to measure vital signs (refer to Sections [5.2.2](#), [5.2.2.1](#) and [5.2.4](#))
8. At Visits 1a and at the EoT / ED visit, a complete physical examination is required. At all other marked visits, a physical examination is only required if the patient reports symptoms. Refer to [Section 5.2.1](#)
9. Pregnancy testing required in women of child-bearing potential (WOCBP) only.  $x_s$  = serum testing;  $x_u$  = urine testing. Serum pregnancy will be done at screening (Visit 1a) and as a reflex when urine testing is positive. More frequent pregnancy testing should be done if required by local regulation and /or authority or per investigator judgement. Pregnancy testing at dosing visits should be completed prior to administration of trial medication. Refer to [Section 5.2.3](#)
10. Refer to [Section 5.2.5.2](#) for details regarding the necessity for a gastroscopy at Visit 1b
11. For further details regarding the HVPG measurement, refer to [Section 5.1.1](#)
12. For further details regarding ultrasound of the liver and spleen, refer to Section [5.2.5.1](#)
13. [redacted]
14. For further details regarding dose-titration, refer to [Section 4.1.4](#)
15. Electronic home BP monitoring equipment will be provided for a patient to measure BP and HR on a daily basis from Visit 2 (refer to [Section 5.2.2.1](#)). Following training on the use of the equipment at Visit 2, subsequent refresher training should be provided if required
16. A paper patient reminder card will be used to record the time of dosing with trial medication on the 3 days that precede PK sampling visits (refer to Sections [5.3](#), [5.6.1](#) and [Appendix 10.1](#)). Following training on completion of the diary at Visit 2, subsequent refresher training should be provided if required
17. Biomarker sampling requires a consistent status from one sample to another in terms of fasting vs non-fasting; a fasting status is therefore defined. For further details regarding sampling, refer to [Section 5.4](#).
18. PK sampling: except for the EoT visit, samples will be collected pre-dose, and at 30 minutes, 1 hour and 2 hours post-dose. At the EoT visit, only a pre-dose sample will be collected. The time of dosing with trial medication will be recorded on the 3 days that precede PK sampling visits. Refer to Sections [5.3](#), [5.6.1](#) and [Appendix 10.1](#)
19. Biobanking sampling requires a consistent status from one sample to another in terms of fasting vs non-fasting; a fasting status is therefore defined. Sampling is optional and requires separate informed consent. Refer to [Section 5.5](#)
20. After the EoS visit (= individual patients end of the trial) the Investigator should report only the following: any cancers of new histology and exacerbations of existing cancer, trial medication related Serious Adverse Events (SAEs) and trial medication related Adverse Events of Special Interest (AESIs) of which the Investigator may become aware of. These should be reported only via the BI SAE form (refer to [Section 5.2.6.2.1](#))
21. The physical examination at Visit 1a should include an assessment of the clinical criteria for Child-Turcotte-Pugh classification (refer to [Appendix 10.3](#))

Proprietary confidential information © 2023 Boehringer Ingelheim International GmbH or one or more of its affiliated companies

22. During the dose-titration period (i.e. when up-titration is occurring), and at the subsequent visit, vital signs and 12-lead ECGs will also be repeated approximately 1 hour and 2 hours after intake of the trial medication. Measurement of vital signs should precede the 12-lead ECG, and measurement of the 12-lead ECG should precede the 1 hour and 2 hour post-dose PK samples (refer to Sections [5.2.2](#), [5.2.4](#) and [5.3](#)).

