#### **2.1.3 Secondary endpoint(s)**

Secondary endpoints include:

- occurrence of a response, which is defined as > 10% reduction from baseline HVPG (measured in mmHg) after 8 weeks of treatment
- occurrence of one or more decompensation events (i.e. ascites, VH, and / or overt HE) during the 8-week treatment period
- occurrence of CTCAE grade 3 (or higher) hypotension or syncope based on Investigator judgement, during the 8-week treatment period
- occurrence of discontinuation due to hypotension or syncope during the 8-week treatment period

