### 3.3.4.1 Discontinuation of trial treatment

Ideally, the patient should attend all remaining visits. Should the patient not agree, at least phone contacts should occur at the scheduled visit time points, should that not be acceptable, a phone contact once a year or at the end of the planned observation period should occur to collect the most relevant information: vital status (please see [section 5.2.6.2.1](#) ), outcome events, adverse events, or last contact date in case of lost to follow-up.

An individual patient will discontinue trial treatment (BI 685509 and empagliflozin) if:

- the patient wants to discontinue trial treatment. The patient will be asked to explain the reasons but has the right to refuse to answer.
- the patient has repeatedly shown to be non-compliant with important trial procedures and, in the opinion of both the investigator and sponsor representative, the safety of the patient cannot be guaranteed as he / she is not willing or able to adhere to the trial requirements in the future.
- the patient needs to take concomitant medication that interferes with the safety/efficacy of the investigational medicinal product or other trial treatment (refer to [Section 4.2.2.1](#)). If short-term, acute use of a restricted concomitant therapy is required (e.g. 5-7 days of antibiotic treatment for an infection), this will not automatically require discontinuation of BI 685509 or empagliflozin. Similarly, if a patient needs to modify a dose, where only a stable dose is permitted (e.g. NSBBs / carvedilol, statins, anti-viral therapy for HBV, pioglitazone, GLP1-agonists, or vitamin E), this also will not automatically require discontinuation. In both cases, the Sponsor should be consulted.
- the patient experiences a severe infection, e.g. with SARS-CoV-2, as determined by the Investigator
- the patient meets the criteria for hepatic injury (refer to [Section 5.2.6.1.4](#) and [Appendix 10.2](#))
- the patient has an acute liver decompensation event such as VH, new-onset of ascites, new-onset of overt encephalopathy, or other new-onset decompensation event based on Investigator judgement
- patients with worsening of their liver function (e.g. from Child-Turcotte-Pugh A to Child-Turcotte-Pugh B with clinical evidence of deteriorating liver function in the opinion of the Investigator). Refer to Child-Turcotte-Pugh classification method in [Appendix 10.3](#)

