#### 4.1.4.1 Rules for down-titration in case of intolerance to BI 685509

If a patient has an AE that, based on Investigator judgement, may be related to trial medication, the down-titration rules below must be followed. These rules apply if the patient has successfully completed the dose titration period (i.e. Visit 4) and is either still taking their final assigned dose of trial medication, or if they have missed  $\leq 3$  consecutive doses. If the patient has not successfully completed the dose titration period (i.e. Visit 4), down-titration is not permitted; in case of persistent AEs or severe effects, the patient must permanently discontinue treatment (refer to [Section 3.3.4.1](#)).

- if the patient is receiving [REDACTED] BID BI 685509 the dose will be down-titrated one level to [REDACTED] BID BI 685509

Once down-titration has taken place, no further up-titration will be permitted.

If a patient continues to have an AE, or a new AE develops, that based on Investigator judgement, may be related to trial medication, a second down-titration will be permitted:

- if the patient is receiving [REDACTED] BID BI 685509 the dose will be down-titrated to [REDACTED] BID BI 685509

Down-titration must not be performed by taking less than the two daily doses or by splitting tablets so that a whole tablet is not taken. Down-titration will be managed through the IRT system (refer to [Section 4.1.4](#)). After the successful completion of the dose titration period (i.e. Visit 4), in case of persistent AEs despite down-titration, or severe effects at any dose, permanent treatment discontinuation should be considered (refer to [Section 3.3.4.1](#)). Patients who are down-titrated will need to return to the investigational site to receive their continuing supply of trial medication, either at the next scheduled visit or via an unscheduled visit.

 One dose refers to an individual time point e.g. morning dose or evening dose.

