### 5.2.6.2 Adverse event collection and reporting

#### 5.2.6.2.1 AE collection

The investigator shall maintain and keep detailed records of all AEs in the patient files. The following must be collected and documented on the appropriate CRF(s) by the investigator:

- From signing the informed consent onwards until the individual patient's end of trial (= the End of Study (EoS) visit):  
all AEs (serious and non-serious) and all AESIs.
- After the individual patient's end of trial:  
the investigator does not need to actively monitor the patient for new AEs but should only report any occurrence of cancer and trial drug related SAEs and trial drug related AESIs of which the investigator may become aware of by any means of communication, e.g. phone call. Those AEs should be reported on the BI SAE form (see [section 5.2.6.2.2](#)), but not on the CRF.

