### **6.2.3 Follow-up period and trial completion**

An EoS visit should be scheduled 4 weeks after an EoT and / or ED visit (refer to the [Flow Chart](#) and [Section 3.3.4](#)); participation in the trial is over once this visit has been completed; completion must be recorded on the corresponding eCRF.

When an EoS visit is performed after an ED visit, the assessments performed at the EoS visit should be in accordance with the Flow Chart, with the following exceptions:

- [REDACTED]

Trial completion is defined as a patient who completes the EoS visit within the specified time window and who has not discontinued trial medication prematurely. Following an EoS visit, the patient will return to standard medical care.

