V2	Week 0	Day 1	N/A	1	1	≤1	1
V3	Week 1	Day 8	+2	8	10	2	11
V4	Week 2	Day 15	[contact]
V5	Week 4	Day 29	[contact]
V6	Week 6	Day 43	±3	40	46	37	50
V7	Week 8/ EoT	Day 57	±3	54	60	51	Study medication stop date + X C days
Off-treatment							
V8	Week 12/ EoS	Day 85	±5	80	90	Study medication stop date + X days+1	Day of last follow-up

A In case of premature discontinuation of the study medication, an early EoT visit has to be performed within 7 days of medication stop date. If such an EoT Visit falls into the time window of a previous visit, measurements will be assigned to this previous visit and the visit value will be determined as described above. In this case, the time window for the visit that includes the early EoT visit will end X days after the study medication stop date, including Day X. Patients will then be asked to continue in the study according to the visit schedule. Off-treatment measurements will be assigned to visits in the same manner.

B Days are counted relative to the day of first treatment, which is defined as Day 1.

\* Start (extended): End of extended window of last visit+1

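### The early-discontinuation visit rules can end active AE collection before Day 57, while other passages keep the patient on schedule, so two 8-week secondary endpoints may not be observed for 8 weeks

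*Protocol*

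**What the plan says.** **Rules that bring the final visit forward.** In Flow Chart footnote 3, patients who complete treatment "will have an End of Treatment (EoT) visit, followed 4 weeks later by an End of Study (EoS) visit"; the planned days are 57 and 85. For patients who stop early: "The ED visit should be performed within 7 days of discontinuing the trial medication, followed 4 weeks later by an EoS visit". Protocol 6.2.2.1 puts the ED visit in place of the planned treatment visit. The later part of 3.3.4.1 and Section 6.2.3 repeat the 4-week interval to EoS, and 6.2.3 adds that "participation in the trial is over once this visit has been completed". From then on, under 5.2.6.2.1, "the investigator does not need to actively monitor the patient for new AEs". Only cancers and drug-related SAEs and AESIs that come to the investigator's attention are still reported, and these do not go on the CRF.

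**Rules that keep the patient on schedule.** Protocol 3.3.4 asks patients who stop treatment to come to further visits if they agree. Section 3.3.4.1 opens: "Ideally, the patient should attend all remaining visits". If the patient declines, it asks for phone contact at the planned visit times. Failing that, it asks for a contact yearly or at the close of planned observation, covering outcome events and AEs. SAP Table 6.7:2 footnote A, on early discontinuation, says: "Patients will then be asked to continue in the study according to the visit schedule".

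**Endpoints and analysis.** Protocol 2.1.3 lists "occurrence of one or more decompensation events (i.e. ascites, VH, and / or overt HE) during the 8-week treatment period". It also lists grade 3 or higher hypotension or syncope, and discontinuation due to either, over the same period. Protocol 7.2.2 and SAP 6.3 handle premature discontinuation by treatment policy. SAP Section 7 bases percentages on every patient in the analysis set, with or without data. SAP 7.8.2.1 assigns AEs later than 7 days after the last dose to follow-up, for listings only.

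**The concern.** Treatment policy means that what happens after a patient stops still counts, so the patient has to be observed to the end of the endpoint period. If EoS is tied to the ED visit and ends participation, a patient who stops in the first weeks leaves active AE collection before Day 57. A decompensation in the remaining days, or a grade 3 or higher hypotension or syncope not judged drug-related, need not be recorded. The patient nevertheless stays in the denominator and appears event-free.

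The titration phase deserves attention. Until Visit 4 is completed, down-titration is not available, and Protocol 4.1.4.1 says "in case of persistent AEs or severe effects, the patient must permanently discontinue treatment". A stop under that rule falls at a time when the early EoS lies well before Day 57. The patients concerned would be those who tolerated the drug poorly, so the shortened observation would not be random. Data that were never collected cannot be recovered by a later choice in the SAP.

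**Working it through.** **Inputs.** Flow Chart: Visit 3 on Day 8, Visit 4 on Day 15 (window +2, so Day 17 at latest), EoT on Day 57, EoS on Day 85 (window ±5). Footnote 3: ED 0 to 7 days after stopping, EoS 28 days after ED. SAP 7.8.2.1: AEs counted as on-treatment to last dose + 7 days.

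**The plan's own figure.** Completers: 57 + 28 = Day 85, which matches the Flow Chart.

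**Early stoppers.** Let s be the day of stopping, taken as the last-dose day.

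- ED = s to s + 7
- Nominal EoS = s + 28 to s + 35
- Days from EoS to Day 57 = 57 − (s + 35) to 57 − (s + 28)
- Latest EoS using the full +5 window = s + 40
- End of the SAP's general AE window = s + 7

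| Stop day s | Nominal EoS | Days from EoS to Day 57 | Latest EoS with +5 | End of SAP AE window |
|---|---|---|---|---|
| 1 | 29–36 | 21–28 | 41 | 8 |
| 8 | 36–43 | 14–21 | 48 | 15 |
| 15 | 43–50 | 7–14 | 55 | 22 |
| 17 | 45–52 | 5–12 | 57 | 24 |
| 21 | 49–56 | 1–8 | 61 | 28 |
| 28 | 56–63 | −6 to 1 | 68 | 35 |

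**Limits on nominal dates.** With the latest ED visit, s + 35 < 57 gives s ≤ 21. With ED on the day of stopping, s + 28 < 57 gives s ≤ 28.

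**Share of the period.** For a stop on Day 8, 14/56 = 25% to 21/56 = 37.5% of the 8 weeks falls after the final visit.

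**Under the other passages.** If the patient keeps the planned schedule, the last visit is Day 85 and the 8 weeks are covered. The gap exists only under the ED/EoS rules.

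**Weight of one event.** In a group of 20, one missed event is 1/20 = 5 percentage points. This assumes that an event does occur in the gap.

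**The case against.** The strongest reply is that the protocol already asks for most of the remedy. Day 57 is a planned visit time, and 3.3.4.1 wants at least a phone contact then. This stands as evidence of intent. It does not settle the matter, because the same section also contains the ED-plus-4-weeks rule and 6.2.3 closes participation at that EoS. A site that works from the Flow Chart commits no deviation and makes no further contact.

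Some stronger readings are tempting, and the documents do not support them:

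- *A site cannot follow both sets of rules.* Footnote 3 replaces a single planned visit, and SAP footnote A describes an early EoT visit followed by continued visits. The obstacle is the EoS timing together with the statement that participation is then over.
- *The early EoS by itself biases the reported percentages downwards.* The decompensation categories in SAP 7.5.3 are coded AE terms, and hypotension and syncope come from AE reports. If the general rule of last dose plus 7 days governs these endpoints, every early stopper is observed throughout the counted window: nominal EoS is at least 28 days after the stop. Longer collection would then only add listed events. The SAP does not say which window applies, so the bias cannot be attributed to visit timing alone.
- *Most stops will occur in titration, because intolerance then forces discontinuation.* No rate is given. Protocol 4.1.4.1 covers only persistent AEs or severe effects; 4.1.4 allows interruption and restart, and 4.1.4.2 allows a patient to be held at the current dose. In the interim data from Trial 1366-0020 (Protocol 1.2.1), orthostatic intolerance led to no discontinuation.

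It also stands that the analyses are descriptive, and that hypotension or syncope lost in the gap would occur about four weeks or more after the last dose, against a residual effect period of 7 days.

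**Conclusion.** The contradiction is in the current text and the calendar arithmetic holds. Under the ED/EoS rules, active AE collection ends before Day 57 for every stop up to Day 21, and up to Day 28 when the ED visit is prompt, before the ±5-day EoS window is applied. The full +5 days does not close the gap for a stop on Day 15 and only just reaches Day 57 for a stop on Day 17 with the latest ED visit.

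Two endpoints are exposed: decompensation, and grade 3 or higher hypotension or syncope. Discontinuation due to hypotension or syncope is not affected, since it is known once the patient stops. A patient who stopped because of decompensation already has that event. The primary endpoint is not at issue here.

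The conclusion takes the 8-week treatment period to run to Day 57 whether or not treatment continues, which is what treatment policy implies but neither document states. The number of patients affected, and any effect on the percentages, cannot be computed: the documents give no discontinuation rate and no event rate for the gap. The point should be corrected because the loss cannot be repaired afterwards and prevention is cheap.

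**What to change.** **Protocol.** Reconcile Flow Chart footnote 3, 6.2.2.1, 6.2.3 and the ED/EoS paragraph of 3.3.4.1 with 3.3.4, the opening of 3.3.4.1 and SAP Table 6.7:2 footnote A. The reconciled text should say that the contacts in 3.3.4.1 continue after an early ED or EoS visit, and that active collection of AEs and decompensation events runs at least to Day 57. A phone contact is enough at Day 57. Because the concomitant-therapy restrictions in 4.2.2.1 run to EoS, the text should also say whether they move if EoS moves.

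**SAP.** State in 7.5.3 that decompensation and grade 3 or higher hypotension or syncope are counted to Day 57 regardless of discontinuation, and that the last-dose-plus-7-days rule of 7.8.2.1 does not limit them. The two changes belong together.

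**Cost.** Wording in both documents, one phone contact per patient who stops before about Day 29, and up to about 4 more weeks of follow-up (57 − 29 = 28 days for a stop and ED visit on Day 1). No added procedure is needed.
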